7.6 Protocol Deviations

In randomized subjects, numbers and proportions of subjects with major deviations from the protocol will be determined for each deviation category (treatment-related deviations, eligibility-related deviations, a failure to discontinue the trial when the subject meets the withdrawal criteria, procedure-related deviations that affect evaluation of the primary endpoint, use of prohibited medications, and overall) and each trial site, overall, for each treatment group, and for the overall brexpiprazole group.

In non-randomized subjects, similar summarization will be performed overall and for each requisite concomitant medication.

8 Efficacy Analysis

Efficacy analysis in the double-blind period (Phase B) will be performed using the FAS. Unless otherwise stated, the efficacy analysis described in this section relates only to the double-blind period (phase B).

8.1 Primary Efficacy Endpoint

The primary endpoint is mean changes from baseline (Week 8 of the antidepressant treatment period [Phase A]) in MADRS total scores at Week 6 of the double-blind period (Phase B).

8.1.1 Primary Efficacy Analysis

For the primary analysis, MMRM analysis will be performed using the OC data set in the FAS. The statistical hypotheses will be tested, based on differences in least square means between each brexpiprazole group and the placebo group, which are calculated by MMRM. To adjust for multiplicity of tests, due to there being 2 comparisons with the placebo group for each of the brexpiprazole groups, a fixed-sequence approach will be used to control overall type 1 error rates. Comparison between the brexpiprazole 2 mg/day group and placebo group will be performed first; only when significance is observed at a two-sided significance level of 5%, will comparison between the brexpiprazole 1 mg/day group and placebo group be performed at a two-sided significance level of 5%.

The MMRM will include treatment group (brexpiprazole 1 mg/day group, brexpiprazole 2 mg/day group, and placebo group), time point (double-blind period [Phase B] Weeks 1, 2, 3, 4, 5, and 6), and interaction between treatment group and time point as factors, and baseline and interaction between baseline and time point as covariates. Unstructured error variance-covariance structure will be assumed. For a degree-of-freedom approximation,

the Kenward-Roger method will be used. If any problems in convergence status arise in the estimation of variance components, heterogeneous Toeplitz, heterogeneous autoregressive of order 1, and heterogeneous compound symmetry, which are error variance-covariance structures, will be applied in this order, and the first structure that achieves convergence will be used in the primary analysis. If anything other than an unstructured variance-covariance structure is selected, a sandwich estimator for standard errors will be used.

For each time point, least square means of each treatment group and differences in least square means between each brexpiprazole group and the placebo group, as well as the two-sided 95% confidence intervals (CIs) will be determined.

8.1.2 Sensitivity Analyses

8.1.2.1 Sensitivity Analysis for Handling of Missing Data

As a sensitivity analysis for handling of missing data, placebo multiple imputation and tipping point analysis on MNAR assumption will be performed using a pattern-mixture model with multiple imputation.

Multiple imputation analysis will be performed according to the following procedure. The number of imputations will be 100.

- 1) The Markov Chain Monte Carlo (MCMC) method will be used to impute intermittent missing data to produce a monotone missing data pattern.
- 2) The monotone regression method will be used to impute monotone missing data.
- 3) The same MMRM as that of the primary efficacy analysis will be used to analyze the multiple-imputed datasets.
- 4) The MIANALYZE procedure will be used to integrate the analysis results of the multiple-imputed datasets, and the estimate of the difference between each brexpiprazole group and the placebo group at Week 6 in the double-blind period (Phase B) and its 95% CI and p-value will be determined.

In placebo multiple imputation, for discontinued subjects in each brexpiprazole group, MNAR will be assumed for missing data after discontinuation and an imputation model based on the placebo group will be used in imputation.

In tipping point analysis, for subjects in each brexpiprazole group who discontinued treatment for any of the following reasons, MNAR will be assumed for missing data after discontinuation.

- Withdrawal for any reason
- Withdrawal due to AEs, a lack of efficacy, or consent withdrawal
- Withdrawal due to AEs or a lack of efficacy

For subjects in each brexpiprazole group who discontinued treatment for reasons assumed as MNAR, the MAR assumption will be used to impute post-discontinuation missing data, add Δ (intergroup differences in MMRM of the primary efficacy analysis) \times k% to the imputed value, and increase k until a statistically significant conclusion is reversed ($p > 0.05$).

8.1.2.2 Sensitivity Analysis for Normality Assumption

As a sensitivity analysis for normality assumption, multiple imputation under the MAR assumption will be performed, and the Wilcoxon rank sum test will be used to compare each brexpiprazole group and the placebo group for each time point, and the Hodges-Lehmann estimator of the intergroup difference will be determined. A robust regression analysis with treatment group as a factor and baseline as a covariate will also be performed for each time point. Similar analysis without multiple imputation will also be performed.

8.1.3 Technical Computational Details for Primary Efficacy Analysis

The SAS code for the MIXED procedure to perform the primary efficacy MMRM analysis is shown below.

```
proc mixed;
  class treatment visit subjid;
  model change=treatment visit baseline treatment*visit baseline*visit / ddfm=kr;
  repeated visit /type=un subject=subjid;
  lsmeans treament*visit / diff cl;
  ods output diffs=diffs lsmeans=lsmeans;
run;
```

8.2 Secondary Efficacy Analyses

- MADRS response rate at Week 6 of the double-blind period (Phase B)
- MADRS remission rate at Week 6 of the double-blind period (Phase B)
- CGI-I improvement rate at Week 6 of the double-blind period (Phase B)

For the MADRS response rate, a χ^2 test will be performed for between-treatment-group comparison using the LOCF data set. Differences in the response rates between each of the brexpiprazole groups and the placebo group, and the two-sided 95% CIs (Wald confidence interval) will be determined. For MADRS remission rate and CGI-I

improvement rate, the same analysis employed for the MADRS response rate will be used. The same analysis will be performed on the OC dataset.

- Mean changes from baseline (Week 8 of the antidepressant treatment period [Phase A]) in HAM-D 17-item total scores at Week 6 of the double-blind period (Phase B)
Using the LOCF data set, analysis will be performed by ANCOVA model with treatment group as a factor and baseline as a covariate. Least square means of each treatment group and differences in least square means between each brexpiprazole group and the placebo group, as well as the two-sided 95% CIs will be determined. The same analysis will be performed on the OC dataset.
- Mean changes from baseline (Week 8 of the antidepressant treatment period [Phase A]) in CGI-S at Week 6 of the double-blind period (Phase B)
- Mean changes from baseline (Week 8 of the antidepressant treatment period [Phase A]) in mean SDS scores at Week 6 of the double-blind period (Phase B)
- Mean changes from baseline (Week 8 of the antidepressant treatment period [Phase A]) in MADRS-S total scores at Week 6 of the double-blind period (Phase B)

As performed for the primary endpoint, MMRM analysis will be performed. Each item on the SDS (work/school, social life, and family life/home responsibilities) will also be analyzed in the same manner.

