3.5.8 Abnormal Involuntary Movement Scale (AIMS)

The AIMS total score will be the sum of scores for AIMS items 1 through 7.

4 Sample Size

In phase 3, double-blind, placebo-controlled, fixed dose trials of brexpiprazole (331-10-227, 331-10-228, and 331-13-214) conducted outside Japan, changes from baseline in MADRS total scores at Week 6 of the double-blind period (Phase B) have been analyzed by the Mixed-model Repeated Measure (MMRM) method (for 331-10-227 and 331-10-228, based on the results for efficacy from an analysis of subgroups meeting the inclusion criteria that had been revised in the middle of the trials), which demonstrated that the differences between the brexpiprazole groups (the 3 mg group in 331-10-227, and the 2 mg group in 331-10-228 and 331-13-214) and the placebo group were -1.9 , -3.2 , and -2.3 , respectively, and that the standard deviations obtained from standard errors and numbers of subjects at Week 6 of the double-blind period (Phase B) were 7.2, 7.7, and 8.2, respectively. On the assumption that the difference in changes from baseline in MADRS total scores at Week 6 of the double-blind period (Phase B) is -2.4 for the brexpiprazole group compared with the placebo group with a standard deviation of 7.7, this trial will require 218 subjects per group to ensure a power of 90% in a two-sided test with a significance level of 0.05. We have decided that the planned number of subjects for randomization will be 240 per group, assuming that 7% of subjects will discontinue the trial during the double-blind period (Phase B) and some subjects will be excluded from analysis.

5 Statistical Analysis Datasets

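### MADRS response and remission at Week 6 are tested without baseline and on LOCF data; adjusting for baseline would add roughly 1 to 6 points of power for remission and 0 to 4 for response, and LOCF costs little at 7% dropout

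*SAP*

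**What the plan says.** For MADRS response, SAP 8.2 prescribes a chi-square: "test will be performed for between-treatment-group comparison using the LOCF data set". It adds the difference in rates from placebo with a Wald 95% interval, applies the same method to remission, and repeats everything on the OC data (tables CT-5.3.2 and CT-5.4.2 in SAP Appendix 5). Protocol 7.4.2 names the same test and data set. No covariate or stratification factor appears.

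The continuous secondary endpoints in the same section do adjust for baseline. For HAM-D: "Using the LOCF data set, analysis will be performed by ANCOVA model with treatment group as a factor and baseline as a covariate". CGI-S, SDS and MADRS-S follow the primary MMRM, which contains baseline and its interaction with visit (SAP 8.1.1).

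Four other places matter:

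- SAP 6.2 defines response as a fall of at least half from baseline; remission also requires a total of 10 or less.
- SAP 5.2 admits a subject to the FAS with one post-baseline MADRS, and SAP 5.6 lets LOCF carry that score forward.
- SAP 5.6 bases the primary analysis on MAR.
- SAP 8.1.2.2 already plans multiple imputation of MADRS under MAR. SAP 8.1.2.1 says of its own imputation procedure: "The number of imputations will be 100".

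**The concern.** Two features of the test do not fit the rest of the plan.

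**Baseline is unused.** Remission combines a relative and an absolute condition. Above a baseline of 20, half the baseline exceeds 10, so the fixed cut-off is the one that binds. A subject starting at 22 must fall 12 points (12/22 = 55%); one starting at 30 must fall 20 (20/30 = 67%). Baseline therefore predicts remission, and leaving out a known predictor costs power.

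**LOCF does not measure the endpoint as defined.** The endpoint is status at Week 6, but a drop-out's Week 1 to 5 score can fill that slot. In the 2 mg arm a Week 1 score was obtained on 1 mg/day (SAP 3.2.2). The same MADRS scores are treated as missing at random in the primary analysis, so the two sets of tables rest on different assumptions and could drift apart if dropout differs by arm.

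At stake is the precision and consistency of two supporting efficacy tables.

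**Working it through.** **1. The plan's own figure.** SAP Section 4 sizes the primary endpoint for "a power of 90% in a two-sided test with a significance level of 0.05", with a difference of −2.4 "for the brexpiprazole group compared with the placebo group with a standard deviation of 7.7".

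n = 2(1.960 + 1.282)² × 7.7²/2.4² = 2 × 10.507 × 10.293 = 216.3, so 217 per group by the normal approximation. The t-based calculation gives 218 (power 90.1%; 217 gives 89.96%), matching "this trial will require 218 subjects per group". Allowing for 7% dropout, 218/0.93 = 234.4, so 235; 240 leaves room for exclusions. At 7%, 0.07 × 240 = 16.8 subjects per arm would have a carried-forward score. No rate or power is stated for response or remission.

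**2. Power gained from baseline.** From the documents: 240 per arm, effect −2.4, SD 7.7. Assumed, because the documents do not give them: baseline mean and SD, placebo change, and the link between baseline and change. Each row compares the chi-square with a likelihood-ratio test for treatment in a logistic model containing baseline.

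| Assumptions | Remission power, % | Response power, % |
|---|---|---|
| Mean 27, SD 5 to 7, placebo change −7, baseline–change correlation 0 to −0.4; six settings, 1,500 trials each | 52.1→57.9, 47.5→57.9, 57.5→61.3, 52.0→58.9, 61.6→62.3, 59.9→63.5 | 66.9→69.3, 64.2→68.3, 73.5→73.7, 71.5→72.8, 77.1→76.7, 77.6→77.9 |
| Mean 22, SD 5, placebo change −6.5, slope of change on baseline 0 / −0.3, 7% dropout; 3,500 trials each | 62.1→66.4 / 67.0→69.5 | 69.2→71.4 / 73.2→73.9 |
| As above, mean 26 | 52.6→57.8 / 55.1→57.8 | 65.3→68.3 / 68.3→68.6 |

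In the first row the remission gains are 5.8, 10.4, 3.8, 6.9, 0.7 and 3.6 points; in the other rows they are 2.5 to 5.2. A further run at mean 22 or 27 (SD 5 to 5.5, 1,000 trials per setting) gave 45.9→54.6 and 61.9→65.5, that is, 8.7 and 3.6. Response gains run from −0.4 to 4.1. The Monte Carlo standard error of one power estimate at 1,500 trials is √(0.5 × 0.5/1500) = 1.3 points, so the small response gains are hard to tell from zero.

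*Cross-check.* If baseline explains a share R² of outcome variance, the effective sample size is 240/(1 − R²). For 20% against 30%, power is 71.7% unadjusted and 72.1%, 73.0%, 73.9% and 76.2% at R² of 1%, 3%, 5% and 10%. At means 22 and 26 in the table, R² was about 1% to 5% for response and 5% to 12% for remission, which agrees with the size and order of the gains.

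**3. Shift caused by LOCF.** With random dropout after Weeks 1 to 4 and a full-data response difference of 10.2 points:

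| Dropout, placebo/active | LOCF difference | Shift |
|---|---|---|
| 7%/7% | 9.7 | −0.5 |
| 4%/10% | 8.7 | −1.5 |
| 10%/4% | 10.8 | +0.6 |

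*Consistency check.* Let g be the fall in a drop-out's chance of counting as a responder when an early score replaces Week 6. Then shift = d(placebo) × g(placebo) − d(active) × g(active). The last two rows give g(active) = 20.7 and g(placebo) = 14.3 points. At 7%/7% this predicts 0.07 × (14.3 − 20.7) = −0.45, in line with the −0.5 found. In the 7% dropout runs at means 22 and 26 the shift was −0.3 (for example 9.5 against 9.8).

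**The case against.** A chi-square with a marginal risk difference is a valid randomised comparison; omitting baseline costs efficiency, not validity. The plan also repeats the tests on observed cases, and under purely random dropout that analysis recovers the full-data difference. These points stand, and they limit the matter to efficiency and consistency. They do not remove it. The OC test is also unadjusted, and it requires more than the primary does: MAR allows dropout to depend on earlier scores, whereas a complete-case comparison does not use them. The placebo-based and tipping-point analyses cover only the MADRS total score.

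A reader might infer more than the documents support:

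- **That LOCF flatters the drug.** It did so only when placebo dropout was the higher. Discontinuation for adverse events in the earlier trials mostly runs the other way: 3.5% on 3 mg and 1.3% on 1 mg against 1.4%; 3.2% against 0.0%; 2.1% against 0.5% (protocol 1.2.2). All-cause rates are not given. The largest of these gaps is 3.2 points, so the 6-point gap in 4%/10% is an illustration, not a forecast.
- **That remission loses 10 points of power.** That is the top of a range built on assumed inputs.
- **That CGI-I improvement and HAM-D need the same change.** No CGI-I imputation is planned, and its power loss cannot be computed from the documents. HAM-D is already baseline-adjusted with both LOCF and OC versions planned; promoting OC would only put a completer analysis first.

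**Conclusion.** The point holds as a modest improvement to two secondary analyses. Adding baseline MADRS gains roughly 1 to 6 points of power for remission in most settings examined, with 6.9, 8.7 and 10.4 at the upper end, and about 0 to 4 points for response. These figures depend on assumed baseline, placebo-change and correlation values; only the effect, SD, sample size and 7% dropout come from the plan. No run combined baseline adjustment with multiple imputation, so the gains describe adjustment alone.

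Replacing LOCF is mainly a matter of consistency with the primary: about 0.5 points on the response difference at the planned dropout, and about 1.5 if dropout were 4% on placebo and 10% on active.

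It would be wrong to conclude that the primary result or the control of type I error is affected. SAP 8.1.1 places only the two primary comparisons in the fixed sequence, and SAP Section 4 sets no power target for these endpoints.

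**What to change.** In SAP 8.2, make the main analysis of MADRS response and remission a logistic model with treatment group and baseline MADRS, fitted to outcomes derived from the MAR-imputed totals of SAP 8.1.2.2. The text should state:

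- the number of imputations for 8.1.2.2 (100, as in 8.1.2.1, would be consistent);
- the derivation: response if the imputed Week 6 total is at most half of baseline, remission if it is also at most 10, with a rule on rounding imputed values;
- the estimate: the risk difference from placebo, standardised over the baseline distribution of the FAS, with its 95% CI, a named variance method within each imputed data set (for example the delta method), and pooling by Rubin's rules.

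Keep the LOCF and OC chi-square tests as sensitivity analyses. Leave CGI-I improvement and HAM-D as planned. Record the departure from protocol 7.4.2 in SAP Section 14.

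The cost is SAP wording and a little programming. The main table becomes less directly comparable with LOCF tables, which the retained LOCF analysis covers. The standardised estimate is still a marginal risk difference, so its interpretation does not change.

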8.3 Subgroup Analyses

For the change from baseline (Week 8 of the antidepressant treatment period [Phase A]) in MADRS total score, the same MMRM analysis as that of the primary endpoint will be performed for each of the following subgroups.

For CYP2D6 phenotype, all subjects in the placebo group will be included in each subgroup.

- Requisite concomitant medication (duloxetine, escitalopram, fluvoxamine, milnacipran, paroxetine, sertraline, venlafaxine)
- Sex (male, female)
- Age (< 55 , ≥ 55)
- Number of adequate antidepressant drug treatments (1, 2, 3)
- DSM-5 diagnosis (single episode, recurrent episode)
- Frequency of major depressive episodes (1, 2, ≥ 3)
- Duration (in months) of the current episode (\leq median, $>$ median)
- Baseline MADRS total score (\leq median, $>$ median)

- Concomitant use of ultrashort-acting sedative-hypnotic drugs in the double-blind period (Phase B) (yes or no)
- Body weight (\leq median, $>$ median)
- BMI (\leq median, $>$ median)
- CYP2D6 phenotype (IM, EM)
- Impact of COVID-19 pandemic (subjects from whom consent was obtained before 07 Apr 2020, those from whom consent was obtained on or after 07 Apr 2020)

